1.2 Rationale

The theoretical benefits of catheters with CF sensing technology include feedback to the user of adequate degree of tissue contact to prevent inappropriate RF power application. The data have shown when investigators stay within their pre-selected contact force range > 80% of the time the 12-month effectiveness success rate is consistently above 80%. Additional benefits of confirmed tissue contact may include efficient creation of 3-D anatomical maps with the CARTO® 3 Navigation System(s), and may translate to a reduction in mapping, fluoroscopy, and procedure times. Catheters with THERMOCOOL SMARTTOUCH® technology have been used safely in the paroxysmal AF population.^{23,24}

[REDACTED]

As noted, there are few controlled studies on the effectiveness of RF ablation specifically in the persistent AF population,⁴ but studies which included persistent AF patients in their study sample showed promising results for long-term freedom from AF recurrence in this subset.^{8-11,16} The results of the current study will be compared to a pre-determined performance goal of 40% for primary effectiveness, defined as freedom from atrial tachycardias through 12 months post procedure. This is in line with recommendations in the 2012 HRS/EHRA/ECAS Consensus Statement for success rate in persistent AF and longstanding persistent AF.⁴

In patients with AF, elimination or amelioration of symptoms is a major driving force for therapy. The primary clinical benefit of catheter ablation of AF is an improvement in quality of life resulting from the elimination of arrhythmia-related symptoms such as palpitations, fatigue, or effort intolerance.⁴ The 2012 HRS/EHRA/ECAS Consensus Statement underscores the value of AF-specific QOL assessment tools.⁴ The Canadian Cardiovascular Society Severity of Atrial Fibrillation (CCS-SAF) Scale was validated in

484 patients with documented AF (62% paroxysmal and 38% persistent/permanent).²⁷ As the CCS-SAF class increases from 0 to 4, symptom severity increases.

1.3 Risk Analysis

RF catheter ablation has been used for over 15 years, and the risks and complications are well understood. A summary of risks associated with catheter ablation, including analysis of and plans to minimize these risks is provided below:

1.3.1 Description and Analysis of Risks

Risks associated with catheter ablation

The risk of pulmonary adverse events (e.g. PV stenosis, thrombus and hypertension) associated with an AF ablation procedure targeting the pulmonary veins is considered small (<4%).^{8,9,28-32}

Arterial or venous injury, including arterial dissection, thrombosis, occlusion or hemorrhage at the catheter insertion sites or at other sites along the vessels can occur (risk <1%).^{33,34} These types of injuries may cause hemorrhage, hematoma or ischemic injury to an extremity or major organ.

Risks associated with RF application

RF current may cause occlusion of a coronary artery, either by direct thermal damage, spasm, or thrombosis. Experience at numerous centers suggests that the risk of coronary occlusion is less than 0.5%.^{33,34} Coronary arterial occlusion could produce myocardial infarction, angina or death.

The application of RF current close to the AV node or HIS bundle could damage or destroy the normal AV conduction system, producing complete heart block and requiring implantation of a permanent pacemaker.

A thrombus may form on the ablation electrode during the application of RF current, usually indicated by an impedance rise; however, thrombus may also occur in the absence of an impedance rise. Thrombus may become dislodged and embolize to produce a stroke, myocardial infarction, or other ischemic injuries. Risk of embolus is reduced by quickly terminating the application of current after an impedance rise, which limits the size of the coagulum on the electrode. An important feature of the THERMOCOOL® family of catheters is the absence or very low likelihood of thrombus formation during RF.

Thrombus formation on the endocardium following ablation may produce an arterial or pulmonary embolus. This risk may be reduced by the use of aspirin or other anticoagulant therapy, at the discretion of the investigator.

Cardiac perforation may result from catheter manipulation or application of RF. Published risks of cardiac perforation range from <1% to 2.5%.^{33,34,56,57} This potentially life-threatening injury may result in cardiac tamponade and may require percutaneous pericardial drainage or surgical repair. In the SMART-AF study using the THERMOCOOL SMARTTOUCH® Catheter with contact force sensing technology, there were 4 (2.48%, 4/161) reported incidents of tamponade.⁵¹ Additionally, in the SMART-SF study using a new investigational catheter with contact force sensing technology the observed incidence

of tamponade was 1.3% (2/159). Significant hemodynamic compromise can result in neurologic injury or death. An increased risk of cardiac perforation during ablation may be associated with the use of saline-irrigated electrode catheter due to its ability to create a larger, deeper lesion. This risk is greatest in a thin walled chamber (i.e., right or left atria or right ventricle). However, the risk of perforation related to a deep steam pop is reduced if RF energy is not delivered perpendicular to the wall at power above 35 or 40 watts. If the lesion is deeper the risk of steam pop is higher above 35-40 watts.

Injury to a cardiac valve may result from catheter manipulation or the application of RF current (risk <1%).^{33,34} This may produce valvular insufficiency and possibly require surgical valve replacement.

The application of RF energy along the posterior left atrium can result in thermal injury to the esophagus and the formation of an atrio-esophageal fistula. This is a rare (0.04%) but severe complication of RF ablation requiring surgical intervention or that may result in permanent impairment.³⁵ Reducing power at sites in close proximity to and/or avoiding sites directly over the esophagus may reduce the risk of thermal injury.

Injury to the phrenic nerve may occur as a result of RF application in the region of the right pulmonary veins. The reported incidence of phrenic nerve injury varies from 0% to 0.48% when RF energy is used for catheter ablation.^{36,37} Prior to ablation in the region of the right superior pulmonary vein, precautionary measures such as pacing maneuvers are recommended to evaluate proximity to the phrenic nerve.

Periesophageal vagal nerve injury or pyloric spasm after left atrial catheter ablation of AF can occur when RF energy is applied to the posterior wall of the LA.⁴ While these complications are rare (approximately < 1%), they can potentially compromise the clinical outcome severely, requiring surgical treatment.⁵⁴⁻⁵⁵ While there is no established method to prevent injury to the vagal nerves, the risk may be reduced by using the same techniques used to avoid an atrial esophageal fistula.⁴

Risks associated with the general procedure

Radiation exposure during the fluoroscopic imaging of the catheters may result in an increase in the lifetime risk of developing a fatal malignancy (0.1%) or a genetic defect in offspring (0.002%).³⁶⁻⁴⁰

A patient could develop an allergic reaction to the local anesthetic, sedatives, x-ray dye, heparin, protamine, or other agents administered during the procedure (risk <1%).⁴¹⁻⁴⁵

Hemorrhage could occur as a result of anticoagulation (risk <0.5%), which may require transfusion.^{33,34}

The percutaneous procedure carries risk of infection, either at the catheter insertion site or systemically, including endocarditis and septic emboli (risk <0.5%).^{33,34} This risk can be minimized by using standard aseptic technique and, when indicated, by the use of antibiotic agents.

1.3.2 Minimization of Risks

The risks associated with performing RF catheter ablation using an ablation catheter with CF sensing technology, such as the THERMOCOOL SMARTTOUCH® SF catheter, are

similar to conventional irrigated catheters that do not include this technology. Similarly, the Surround Flow technology found in the THERMOCOOL SMARTTOUCH® SF catheter confers a decreased risk of volume overflow associated events such as CHF and pulmonary edema in patients with impaired LVEF for kidney dysfunction.^{14,17} Data have shown that both the SF and CF technology allow a decrease in overall procedure time in experienced users; this in turn decreases fluoroscopy exposure.¹⁵

The criteria for subject selection, methods, personnel, facilities, and training that have been specified in this study are intended to minimize the risk to subjects undergoing this procedure.

Subjects will be screened prior to treatment in the study to ensure compliance with the inclusion and exclusion criteria. The exclusion criteria have been developed to exclude subjects with a medical history or condition that increases their risk of adverse events (refer to Section 3.1.2 Exclusion Criteria). All subjects will have pre-procedure imaging as described in Section 5.3 to exclude subject that may have LA thrombus, which is intended to decrease the potential for thromboembolic complications.

Investigators will undergo training (refer to Sections 5.17.3 and 9.5) on the use of the THERMOCOOL SMARTTOUCH® SF Catheter with Contact Force Sensing Capability technology prior to subject enrollment.

Investigators experienced in intracardiac mapping and ablation of AF with the use of RF ablation catheters containing contact force technology will be selected for participation in the study. AF ablation procedures will be performed in equipped electrophysiology laboratories with the assistance of nurses and technicians trained in electrophysiology and, as applicable, in the requirement of this protocol.

Should occlusion of a coronary artery occur for any reason, the physician will attempt to restore coronary blood flow through pharmacological, catheter and/or surgical intervention as medically indicated.

Additionally, adverse event data will be evaluated periodically during enrollment and follow-up by an unbiased physician review committee functioning as a Global Safety Monitoring Committee (GSMC) for this study.

1.3.3 Precautions

Invasive electrophysiological evaluation and catheter ablation may impart some degree of risk to the subject. The risk of serious complications is generally related to the severity of cardiac disease. The degree of risk of the electrophysiological and catheter ablation procedures versus the potential benefit of the treatment of a persistent or recurrent arrhythmia should be determined by a qualified physician. Cardiac catheterization and electrophysiological procedures should be performed by qualified and appropriately trained personnel in an electrophysiology laboratory. The laboratory should contain sufficient resuscitative equipment and facilities to manage most potential complications. Failure to observe the contraindications, warnings, and precautions in these instructions and the IFU may result in procedural complications. Immediate risks from ablation treatment may include: cardiovascular injury or perforation with or without cardiac tamponade, pulmonary embolus, tricuspid regurgitation, myocardial infarction, bleeding at the catheter insertion site, sepsis, and death.

Contraindications for catheter ablation of arrhythmia include: existing hemodynamic instability, bacteremia, coagulopathy, prosthetic tricuspid valve, intra-atrial or venous thrombosis, and pregnancy.

■ [REDACTED]

[REDACTED]

[REDACTED]

[REDACTED]

[REDACTED]

[REDACTED]

[REDACTED]

[REDACTED]

[REDACTED]

[REDACTED]

[REDACTED]

[REDACTED]

[REDACTED]

[REDACTED]

[REDACTED]

[REDACTED]

[REDACTED]

[REDACTED]

[REDACTED]

[REDACTED]

[REDACTED]

[REDACTED]

[REDACTED]

[REDACTED]

[REDACTED]

[REDACTED]

[REDACTED]

[REDACTED]

[REDACTED]

[REDACTED]

[REDACTED]

[REDACTED]

[REDACTED]

[REDACTED]

[REDACTED]

[REDACTED]

[REDACTED]

[REDACTED]

[REDACTED]

[REDACTED]

[REDACTED]

[REDACTED]

[REDACTED]

[REDACTED]

1.5 Study Catheters

The THERMOCOOL SMARTTOUCH® SF Diagnostic /Ablation Deflectable Tip Catheters with Contact Force Sensing Capability (D-1347-XX-SI and D-1348-XX-SI) are the only study catheters to be used in this study.

For the remainder of this protocol, “study catheter” will refer to the THERMOCOOL SMARTTOUCH® SF Diagnostic/Ablation Deflectable Tip Catheters with Contact Force Sensing Capability.

Instructions for Use (IFU)

A copy of the IFU for the study catheters and interface cable is included in each product package.

1.6 Supply and Support of Study Catheter

Prior to initiating subject enrollment, Biosense Webster or a representative will provide training to the study site personnel. Investigators selected to participate in the study will have prior experience with the THERMOCOOL SMARTTOUCH® Catheters and received training on the use of the THERMOCOOL SMARTTOUCH® SF Catheter (see Section 5.17.1). The study sites will not be released investigational devices until after receiving IRB approval, signing the clinical study agreement, completing training (may be conducted in parallel with the Site Initiation Visit), and after all other required study start up activities are complete.

2.0 STUDY OBJECTIVE

The purpose of this study is to demonstrate the safety and effectiveness of the THERMOCOOL SMARTTOUCH® SF catheters in the treatment of drug refractory symptomatic persistent atrial fibrillation (PsAF) during standard electrophysiology mapping and RF ablation procedures.

3.0 STUDY DESIGN

The PRECEPT study is a prospective, multicenter, non-randomized clinical evaluation utilizing the THERMOCOOL SMARTTOUCH® SF catheters in treating subjects with symptomatic PsAF who have failed at least one antiarrhythmia drug. Up to 367 subjects will be enrolled at up to 35 sites (approximately 30 US and 5 OUS). Effectiveness and safety endpoints have been defined, and will be compared to predetermined performance goals. Subjects who sign the PRECEPT informed consent are considered enrolled in the study. Enrolled subjects who satisfy all eligibility criteria will then undergo the ablation procedure with the study catheter. After the study ablation procedure, subjects will enter a 3-Month Medication Adjustment Period followed by a 3-Month Therapy Consolidation Period (Day 0-180).

The first 3 months after the ablation procedure, (Medication Adjustment Period; Day 0-90) is intended to allow for modifications to the subject’s medication and allow substrate remodeling to occur. Medication adjustment includes dose modification of currently used AAD or adding new AAD. The following 3-month period (Therapy Consolidation Period; Day 91-180), is to assess the status of the Medication Adjustment Period and perform repeat ablations as necessary. Cardioversion is allowed if the AF recurrence persists during the Therapy Consolidation Period.

After the Therapy Consolidation Period, subjects will enter the Evaluation Period (Days 181-450). Subjects having AF recurrence and/or receiving therapeutic interventions during the evaluation period will be considered effectiveness failures (refer to Section 4.1.1 for all effectiveness failure modes).

All subjects will undergo follow up visits at defined intervals (refer to Table 5-1 Schedule of Treatments and Evaluations). Subjects complete the PRECEPT study after the 15-month follow up visit.

3.1 Subject Selection

3.1.1 Inclusion Criteria

Candidates for this study must meet ALL of the following criteria:

1. Documented symptomatic persistent AF, which is defined as continuous AF sustains beyond 7 days and less than 1 year and is documented by the following:
 - a. Physician's note indicating continuous AF \geq 7 days but no more than 1 year;
AND
 - b. Two electrocardiograms (from any forms of rhythm monitoring) showing continuous AF, with electrocardiogram taken at least 7 days apart⁴ (electrograms cannot be >365 days prior to enrollment)
OR
 - c. 24-hour Holter within 90 days of the ablation procedure showing continuous AF
2. Failed at least one antiarrhythmic drug (AAD) (class I or III) as evidenced by recurrent symptomatic AF, or intolerable to the AAD.
3. Age 18 years or older.
4. Signed Patient Informed Consent Form (ICF).
5. Able and willing to comply with all pre-, post-, and follow-up testing and requirements.

3.1.2 Exclusion Criteria

Candidates for this study will be EXCLUDED from the study if ANY of the following conditions apply:

1. Continuous AF > 12 months (1-Year) (Longstanding Persistent AF)
2. Previous surgical or catheter ablation for atrial fibrillation
3. Any cardiac surgery within the past 2 months (60 days) (includes PCI)
4. CABG surgery within the past 6 months (180 days)
5. Valvular cardiac surgical/percutaneous procedure (i.e., ventriculotomy, atriotomy, and valve repair or replacement and presence of a prosthetic valve)
6. Any carotid stenting or endarterectomy
7. Documented LA thrombus on imaging
8. LA size > 50 mm (parasternal long axis view)
9. LVEF < 40%
10. Contraindication to anticoagulation (heparin or warfarin)
11. History of blood clotting or bleeding abnormalities
12. MI within the past 2 months (60 days)
13. Documented thromboembolic event (including TIA) within the past 12 months (365 days)
14. Rheumatic Heart Disease
15. Uncontrolled heart failure or NYHA function class III or IV
16. Severe mitral regurgitation (Regurgitant volume \geq 60 mL/beat, Regurgitant fraction \geq 50%, and/or Effective regurgitant orifice area \geq 0.40cm²)
17. Awaiting cardiac transplantation or other cardiac surgery within the next 12 months (365 days)
18. Unstable angina
19. Acute illness or active systemic infection or sepsis
20. AF secondary to electrolyte imbalance, thyroid disease, or reversible or non-cardiac cause.
21. Diagnosed atrial myxoma.
22. Presence of implanted ICD/CRT-D.
23. Significant pulmonary disease, (e.g., restrictive pulmonary disease, constrictive or chronic obstructive pulmonary disease) or any other disease or malfunction of the lungs or respiratory system that produces chronic symptoms.
24. Gastroesophageal Reflux Disease (GERD; active requiring significant intervention not including OTC medication)
25. Significant congenital anomaly or medical problem that in the opinion of the investigator would preclude enrollment in this study.
26. Women who are pregnant (as evidenced by pregnancy test if pre-menopausal)
27. Enrollment in an investigational study evaluating another device, biologic, or drug.
28. Presence of intramural thrombus, tumor or other abnormality that precludes vascular access, or manipulation of the catheter.
29. Presence of any other condition that precludes appropriate vascular access.
30. Life expectancy less than 12 months

3.2 Subject Disposition

- **Enrolled Subjects:** subjects who sign the informed consent.
- **Excluded Subjects:** subjects who are enrolled but never undergo insertion of the study catheter.
- **Discontinued Subjects:** subjects who have the investigational catheter inserted but do not undergo ablation (i.e., no RF energy is delivered via the study device). These discontinued subjects will be followed up for 30 days.
- **Lost to Follow-up Subjects:** subjects who are enrolled and have study catheter inserted, but contact is lost after most recent follow-up visit (despite 3 documented attempts).
- **Withdrawn / Early Termination Subjects:** subjects who withdraw consent for study participation or are withdrawn by the investigator or are terminated from the study prior to completion of all follow-up visits.
- **Completed Subjects:** enrolled subjects who completed the 15-month follow-up visit.

3.3 Subject Withdrawal/Early Termination

Subjects may withdraw from the clinical investigation at any time. The decision for the subject to withdraw informed consent must be made independently of influence by the investigator or site personnel. The subject's decision will be documented in the source and eCRF. The investigator may also choose to withdraw a subject from the study if there are safety concerns. If a subject withdraws from the study, the date and reason for withdrawal will be recorded on the appropriate electronic case report form (eCRF).

All data will be collected (as available) until the subject is withdrawn. If the subject is withdrawn due to an adverse event (AE) or serious adverse event (SAE), the investigator should follow the subject until the AE/SAE has resolved or is considered stable.

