7.2 Analyses for Primary Endpoints

7.2.1 Analyses for Primary Effectiveness Endpoint

The null and alternative hypotheses are:

Hypothesis $H_0: P_E \leq 0.40$

$H_a: P_E > 0.40$

P_E : the freedom from documented atrial fibrillation, atrial flutter and atrial tachycardia recurrence at 15 months follow-up

Null hypothesis: The freedom from documented AF/AFL/AT at 15 months is less than or equal to the pre-determined performance goal of 40%.

Alternative hypothesis: The freedom from documented AF/ATL/AT at 15 months is greater than the pre-determined performance goal of 40%.

Analysis Population: The per-protocol population will be used as the primary analysis population. Subjects with missing effectiveness endpoints data during 15 months follow-up period will be excluded from the primary analysis. The subjects who have failed the primary effectiveness endpoint before 15 months will be included in the analysis. Analyses of the primary effectiveness endpoint will be repeated in the mITT population. Sensitivity analyses for missing data will be performed in the PP and mITT populations to assess the impact of missingness on the primary effectiveness outcome and are described in the Statistical Analysis Plan (SAP).

Analysis Method: The primary effectiveness endpoint will be evaluated using the exact test for a binomial proportion at a two-sided significance level of 5%. If the lower bound of the exact two-sided 95% confidence interval of the primary effectiveness endpoint rate is greater than the performance goal of 40%, the study will be considered to have demonstrated effectiveness.

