7.4 Primary Effectiveness Endpoint

Based on a performance goal of 40% and an anticipated freedom from AF recurrence of 50%, 330 subjects will be required to obtain at least 90% power at a two-sided significance level of 0.05 using the exact binomial method.

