9.9 Termination of the Study

The study may be suspended or terminated early at the discretion of the Sponsor, for reasons such as incidence of unanticipated serious adverse device effects that may pose a risk to other subjects. In any early termination, already enrolled subjects will continue to be followed per the study protocol requirements.

Sponsor may also terminate a site prior to completion if it believes the site is no longer capable of participating (e.g., cannot fulfill subject enrollment or protocol compliance goals, site suspension by IRB/REB).

At termination of the investigation, each active site will undergo closeout monitoring to conclude any outstanding issues, resolve all data discrepancies and make sure any outstanding eCRFs are completed, reconcile disposition of investigational devices, discuss responsibilities with the Principal Investigator, and discuss any other items relevant to the conclusion of the study. The termination process will be documented by a written report.

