##### *1) Best-Case Scenario*

Subjects with missing effectiveness outcome will be treated as effectiveness success. The point estimate for freedom from recurrence of atrial tachyarrhythmias and the exact two-sided 95% confidence interval will be presented.

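### Death or investigator withdrawal for safety, with no earlier recorded failure, is not classified for effectiveness; read naturally, the subject leaves the 40% test and is a success in the best case

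*Protocol*

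**What the plan says.** - **Withdrawal.** Protocol 3.3: "The investigator may also choose to withdraw a subject from the study if there are safety concerns". It adds: "All data will be collected (as available) until the subject is withdrawn". If an adverse event was the reason, that event is followed until it resolves or is stable. No other assessment is required after withdrawal.
- **Failure modes.** Protocol 4.1.1 and SAP 6.1.1 list acute procedural, non-study-catheter, repeat-ablation, AAD and surgical failure, besides arrhythmia recurrence on Day 181-450. Death and withdrawal are not listed.
- **Disposition.** Protocol 3.2 and SAP 10.2 have a category that covers investigator withdrawal. No category names death.
- **Primary analysis.** Protocol 7.2.1 uses the per-protocol population and requires the exact two-sided 95% lower limit to exceed 40%. On missing data: "Subjects with missing effectiveness endpoints data during 15 months follow-up period will be excluded from the primary analysis". SAP 10.4.1 agrees. The protocol, but not SAP 10.4.1, adds that subjects who failed before 15 months are kept. Neither document defines missing or says how a death is classified.
- **Sensitivity analyses.** SAP 10.4.3.1 plans four, in both the per-protocol and mITT populations. In the best case, "Subjects with missing effectiveness outcome will be treated as effectiveness success". The worst case scores the same subjects as failures. Multiple imputation uses demographic and baseline characteristics. The tipping-point analysis turns missing values into failures one at a time.
- **Safety.** Table 6-1 makes device- or procedure-related death a primary adverse event.

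**The concern.** Take a subject with entrance block confirmed in all veins who dies of a procedural complication on Day 20. No failure mode applies and no evaluation-period rhythm data exist. Unless someone decides otherwise, the outcome is missing: the subject drops out of the numerator and denominator of the rate tested against 40%, and is credited as arrhythmia-free in the best case. Multiple imputation from baseline variables can also draw a success for this subject, because nothing in the model knows of the death. A subject withdrawn by the investigator for safety is in the same position.

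This kind of missingness follows from a bad course after ablation, so it is unlikely to be ignorable, and excluding such subjects tends to raise the success rate. Because the classification is not written down, it would be settled after the data are known, in an open single-arm trial.

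**Working it through.** **Inputs.** Goal 40%, exact two-sided 95% interval (protocol 7.2.1). Anticipated rate 50%, 330 evaluable subjects (7.4). Attrition at most 10%, 367 enrolled (7.6). *Assumption:* k treated subjects die or are withdrawn for safety with no earlier failure, and none would have been a success. The documents give no rate, so k is a range.

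**1. The plan's own figures.** 330/0.90 = 366.7, rounded up to 367: reproduced. At n = 330, the smallest count whose Clopper-Pearson lower limit exceeds 40% is 151 (45.8%). P(X ≥ 151 | 330, 0.40) = 1.9%. P(X ≥ 151 | 330, 0.50) = 94.5%, which agrees with the stated power of at least 90%.

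**2. Effect of excluding k of 330 treated subjects.** With a true rate of 40% over all 330, expected successes are 0.40 × 330 = 132, so the rate among those analysed is 132/(330 − k). With c the smallest passing count at n = 330 − k, the chance of passing is P(X ≥ c | 330 − k, 132/(330 − k)). The last column is the rate reported for 165 successes, 165/(330 − k).

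| k | n analysed | c | Rate among analysed | Chance of passing | Reported rate |
|---|---|---|---|---|---|
| 0 | 330 | 151 | 40.0% | 1.9% | 50.0% |
| 2 | 328 | 150 | 40.2% | 2.5% | 50.3% |
| 5 | 325 | 148 | 40.6% | 4.1% | 50.8% |
| 10 | 320 | 146 | 41.3% | 6.3% | 51.6% |

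The nominal one-sided limit is 2.5%. Part of the rise is discreteness of the exact test: with no selection at all, P(X ≥ c | n, 0.40) is 2.0%, 2.4% and 2.3% at n = 328, 325 and 320. The remainder is the effect of exclusion. Taking 330 as the number treated is a simplification, since 330 is the evaluable number after attrition.

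**3. Borderline results with all 367 treated.**
- k = 1: no change; 166 successes are needed at both n = 366 and n = 367.
- k = 2: 165/365 = 45.2%, lower limit 40.02%, passes. Counting the two as failures, 165/367 = 45.0%, lower limit 39.8%, fails.

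Two such subjects are therefore enough to change a borderline conclusion.

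**The case against.** Much of the case on the other side stands.

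- **Earlier failures are kept.** A reader might infer that every death or safety withdrawal vanishes. Protocol 7.2.1 rules that out: a subject with acute procedural failure, AF surgery, more than two early repeat ablations, or recurrence after Day 180 remains a failure.
- **Other analyses restore these subjects.** The worst case and tipping point count them as failures, and reasons for missingness are listed by site. This answers transparency but not the decision, because no analysis but the primary one is tied to the claim. The worst case also pools deaths with ordinary loss to follow-up. At the planned rate with 37 missing, 165/367 has a lower limit of 39.8% and misses the goal, so a failed worst case says little about deaths in particular.
- **The best case is meant to be extreme.** It is paired with a worst case and no claim rests on it, so calling it unusable goes too far. In it, these subjects are in the denominator, as successes.
- **Death is not hidden.** Related death is tested in the safety endpoint against 16%. That is a separate hypothesis and does not settle the effectiveness score. Whether death should fail a rhythm endpoint is a choice of estimand, but the choice has to be written down.
- **Section 3.3 is not empty after the procedure.** Up to two repeat study-catheter ablations are allowed to Day 180, so there is something to stop. Nor is scheduled PV-stenosis imaging lost, since imaging is prompted by symptoms.
- **Section 9.9.** On early termination of the study, "already enrolled subjects will continue to be followed per the study protocol requirements". A reader might see a contradiction with 3.3. There is none: 9.9 concerns the study stopping and 3.3 an individual. It shows only that continued follow-up is accepted elsewhere in the plan.

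**Conclusion.** The gap is real and limited. It concerns treated subjects who die, or are withdrawn by the investigator for safety, with no earlier recorded failure. That they count as missing is the natural reading rather than a stated rule, because the documents do not classify them.

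On assumed counts of 2, 5 or 10 of 330, all taken as non-successes, the chance of passing at a true 40% is 2.5%, 4.1% or 6.3% instead of 1.9%. Two subjects remain within the nominal 2.5%, but five do not. Of 367, two can turn a borderline pass into a fail. At the anticipated 50% the conclusion would seldom change: with 2 or 5 of 330 counted as failures and half of the others succeeding, power is P(X ≥ 151 | 328, 0.50) = 93.2% or P(X ≥ 151 | 325, 0.50) = 90.8%.

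A reader might go further and infer that the plan as a whole conceals bad outcomes. The documents do not support that, given the retained earlier failures, the worst-case and tipping-point analyses, and the safety endpoint. The plan should be changed because the correction is cheap and the classification belongs in it before the data are known.

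**What to change.** 1. **Endpoint (protocol 4.1.1, SAP 6.1.1).** Score death adjudicated as device- or procedure-related as an effectiveness failure and keep it in the primary analysis. The relationship is already judged for Table 6-1. That table gives both a seven-day window and an any-time window for death, and the two must be reconciled.
2. **Missing data (SAP 10.4.1, 10.4.3.1).** Define missing. State how other deaths before Day 450 enter the primary analysis. Never impute any death as success, in the best case or in multiple imputation. Repeat in SAP 10.4.1 the protocol rule that keeps subjects who failed before 15 months.
3. **Disposition (protocol 3.2, SAP 10.2).** List deaths as their own category.
4. **Withdrawal (protocol 3.3).** Separate stopping further study-catheter procedures, a clinical decision left to the investigator, from stopping data collection. A treated subject stays on the Table 5-1 follow-up unless consent is withdrawn.

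The cost is wording, with no visits beyond those planned. The observed success rate could fall: with 165 successes, by 50.3 − 50.0 = 0.3 points for two cases and 51.6 − 50.0 = 1.6 points for ten. These are upper figures, because a withdrawn subject who stays in follow-up may still prove a success.
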